**Appendix G: Treatment Response Evaluation**

Study Number: _____ PID: _____	
Investigator: [name]. _____ / _____ / _____ (MM/DD/YYYY)	
Study Visit:  After first-line systemic therapy  Follow-Up: _____ / _____ / _____ (MM/DD/YYYY)  Other visit: (please specify) _____	
Date of Scan: _____ / _____ / _____ (MM/DD/YYYY)	
Imaging Modality:  CT  PET/CT  MRI  Other _____	
Evaluation of Target Lesions	
 Complete Response (CR)  Partial Response (PR)  Progressive Disease (PD):  Stable Disease (SD)  NE	
Evaluation of Non-Target Lesions	
 Complete Response (CR)  Non-CR/Non-PD  Progressive Disease (PD):  NE	
Overall Response this Visit	
 Complete Response (CR)  Partial Response (PR)  Progressive Disease (PD): Date of progression _____ / _____ / _____  Stable Disease  NE	
Treating Physician Signature: _____ Date: _____ / _____ / _____	
PI Signature: _____ Date: _____ / _____ / _____	

**Appendix H: NCI Comorbidity**

**Instructions:** Fill this form out to record comorbidities.

1. Medical Comorbidities

- Acute Myocardial Infarction (1)
- History of Myocardial Infarction (1)
- Congestive Heart Failure (1)
- Peripheral Vascular Disease (1)
- Cerebrovascular Disease (1)
- Chronic Obstructive Pulmonary Disease (COPD) (1)
- Dementia (1)
- Paralysis (Hemiplegia or Paraplegia) (2)
- Diabetes (1)
- Diabetes with Complications (2)
- Renal Disease (2)
- Mild Liver Disease (1)
- Moderate/Severe Liver Disease (3)
- Peptic Ulcer Disease (1)
- Rheumatologic Disease (1)
- AIDS (6)

(Additional): \_\_\_\_\_

**Appendix I: Pulmonary Function Testing**

PID Number \_\_\_\_\_

DOB \_\_\_\_\_

1. Date of Test / /

5. Forced Vital Capacity (FVC): \_\_\_\_\_ Liters

6. Observed Forced Expiratory Volume in first second (FEV1): \_\_\_\_\_ Liters

7. Predicted FEV1: \_\_\_\_\_ Liters

8. % Predicted FEV1: \_\_\_\_\_ %

9. DLCO/VA: \_\_\_\_\_ %

A Randomized Trial of Consolidative Immunotherapy with vs without Thoracic Radiotherapy and / or Stereotactic Body Radiation Therapy (SBRT) after First-line Systemic Therapy for Metastatic NSCLC  
Wake Forest Baptist Comprehensive Cancer Center  
WFBCCC # 62718

**Appendix J: Follow-up Collection Form**

PID Number _____	DOB _____
1. Date of follow-up	_____/_____/_____(MM/DD/YYYY)
2. Visit Interval	Interval from date of day 1 of cycle 1 of chemo immunotherapy: _____ days
3. Were there any delayed patient complications related to the radiotherapy procedure since the last visit? Y*/N	If yes, complete AE form
4. Since the last visit have there been any additional chemotherapy? Y*/N	If yes, specify agents used:
5. ECOG Performance Status _____	
6. Weight (lbs) _____	
7. Height (inches) _____	
NEW THERAPIES	
8. Is the patient receiving any new therapies for lung cancer? Y*/N	
If yes, what therapies specifically _____	

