## 6.0 Pembrolizumab

In order to maintain dose-intensity and cumulative dose-delivery, reasonable efforts should be made to minimize dose reductions and treatment delays. Any subject whose treatment is delayed should be evaluated on a weekly basis until adequate hematologic and non-hematologic parameters have been met. Patients may elect to delay doses of maintenance treatment for up to 3 weeks due to personal preference and this will not constitute a protocol deviation.

Toxicities may require the dose reduction of one or more of the study required medications. The investigator will carefully assess all treatment associated toxicities and, whenever possible, determine if the toxicities can reasonably be attributed to a single agent or a causal relationship with one of the agents can reasonably be ruled out. If appropriate, dose reductions should not affect the dose of other products.

CTC-AE measures will occur at each cycle of consolidation immunotherapy. Dose modifications and treatments for adverse events will be managed at the discretion of the treating physicians per their standard practice. Guidance statements regarding dose modifications and ae management are provided as suggestions for treating physicians but are not mandatory. Reasons for dose delays, dose modifications, or addition of steroid treatments must be documented by the treating physician.

- Toxicity grades are defined using the National Cancer Institute Common Terminology Criteria for Adverse Events (NCI-CTCAE) version 5.0
- Dose escalations are not allowed

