## 8.0 Study Activities and Patient Assessment

### 8.1 Study Calendar

Study	Details	Enrollment 	Prior to Randomization	1 mo F/U 	Every 3 mo For 3 years	Every 6 mo For 2 years
History, Physical		All		PE PS	PE PS	PE PS
PFT's (Spirometry, Lung volume & DLCO)			X 			
RT-related Toxicities and Immunotherapy related toxicities	Graded per NCI CTCAE, v. 5.0	X 		X	X	X
MRI of Brain FDG PET/CT Base of skull to mid-thigh			X 			
CT of Chest Abdomen and Pelvis	To include lungs, liver, and adrenal glands	X 		X 	X 	X 
Serum or urine pregnancy test	Within 1 week prior to RT (if childbearing potential)	X				
Blood sample collection			X	X		
Response Assessment	Determined by a radiologist utilizing RECIST criteria	X		X	X	X
Appendix H		X				
Appendix C,D			X			
Appendix E				X		
Appendix F				X		
Appendix G, J, L				X	X	X

1. Enrollment and randomization must occur after completion of 4 cycles of standard of care systemic therapy, but no later than 180 days from the first day of cycle 1 of standard of care systemic therapy. Randomization will occur no later than 21 days from time of enrollment.
2. CT Chest Abdomen pelvis demonstrating no evidence of progression per RECIST v1.1, must be performed after completion of 4 cycles of standard of care systemic therapy prior to enrollment. Ideal if CT prior to enrollment has IV contrast but not required.
3. PFTs within at least **6 months** of enrollment
4. Baseline evaluation should document any residual toxicity from previous therapies.
5. PET and MRI brain must be completed prior to randomization.
  - a. If PET has been performed within 30 days of enrollment, scan does not need to be repeated.
  - b. If MRI brain has been performed within 90 days of enrollment, scan does not need to be repeated.
6. Followup CT Chest abdomen pelvis to be performed with IV contrast unless medically contraindicated by renal function or contrast allergy.
  - a. For patients randomized to the radiation arm – the first CT will be performed 1 month after the last treatment of radiation per standard of care
  - b. For patients randomized to the immunotherapy arm – the first CT will be performed 1 month after the completion of the 2nd cycle of immunotherapy per standard of care

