**9.2 Adverse Event List for Pembrolizumab**

In general, immunotherapy has a risk (>10%) of developing autoimmune complication(s), such as inflammation of the thyroid (hypothyroidism or hyperthyroidism), colon (colitis), lungs (pneumonitis), liver (hepatitis), or pituitary gland (hypophysitis), which can lead to the symptoms noted below. Autoimmune complications can potentially be life-threatening or permanent. In some cases they may be reversible with urgent administration of steroids and/or other immunosuppressant(s).
	
More common (>10% of patients): 
 
constipation
 
depressed mood
 
diarrhea
 
dry skin and hair
 
feeling cold
 
flushing
 
hair loss
 
hoarseness or husky voice
 
	Less common (<10% of patients): 
 
general feeling of discomfort or illness
 
fever
 
nervousness
 
pain symptoms
 
sensitivity to heat or cold
 
slowed heartbeat
 
stomach cramps
 
sweating
 

A Randomized Trial of Consolidative Immunotherapy with vs without Thoracic Radiotherapy and / or Stereotactic Body Radiation Therapy (SBRT) after First-line Systemic Therapy for Metastatic NSCLC  
Wake Forest Baptist Comprehensive Cancer Center  
WFBCCC # 62718

• joint or muscle pain

• muscle cramps or stiffness

• skin rash or itching

• unusual tiredness or weakness

• stuffy or runny nose

	

• swelling of the face, feet, or lower legs

• tenderness

• cough or thickening of bronchial secretions

• trouble breathing, chest pain, or chest tightness

• trouble sleeping

• upper right abdominal or stomach pain

• watery or bloody diarrhea

• weight change

• yellow eyes and skin

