**Appendix F: 30-day Treatment Follow-up Form**

Definition of 1 mo. or 30 day followup

1. For patients randomized to RT, this time point is considered 30 days +/- 14 days from end of all radiation therapy treatments
2. For patients randomized to immunotherapy alone, this time point is considered 30 days +/- 14 days from the end of the 2nd cycle of on protocol maintenance immunotherapy

Study Number: \_\_\_\_\_ PID: \_\_\_\_\_

Investigator: [name] M.D. Date: \_\_\_\_ / \_\_\_\_ / \_\_\_\_ (MM/DD/YYYY)

**Instructions:** Complete this form to follow-up with patients for adverse events.

**Name of Person Competing form** \_\_\_\_\_

**Did the subject have any adverse events in the last 30 days?** Yes  No

If yes, please report on AE log in WISER

(Note\*: If an SAE occurs in this period, report the event as required in Appendix S):

**Was the subject removed from the study?** Yes  No

If yes, complete the Off-Study Form

**Did the subject withdraw from the study?** Yes  No

If Yes, complete the Withdrawal of Consent Form

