All Adverse Events (AEs) and Serious Adverse Events (SAEs) that occur on any patients enrolled on WFBCCC Investigator Initiated Interventional trials must be entered into the WISER system. The only exception to this requirement is for patients enrolled on NCORP trials at non- WFBCCC sites. AEs and SAEs for NCORP patients enrolled at WFBCCC sites must be entered into the WISER system. Once these AEs and SAEs are entered in WISER, certain actions must be taken regarding the reporting of specific Adverse Events to the DSMC.

All Adverse Events that occur during protocol intervention (defined below) and are coded as either 1) **unexpected grade 4, 2) unplanned inpatient hospitalization > 24 hours (regardless of grade)**, or **grade 5 (death)** must be reported to the DSMC using the SAE console in WISER.

A research nurse or clinical research coordinator when made aware that an adverse event meets one of the above criteria has occurred on a WFBCCC Investigator Initiated interventional trial, is responsible for informing a clinical member of the DSMC by phone (or in-person) about the adverse event. The nurse/coordinator should contact the treating physician prior to calling the DSMC clinical member to obtain all details of the SAE, as well as all associated

A Randomized Trial of Consolidative Immunotherapy with vs without Thoracic Radiotherapy and / or Stereotactic Body Radiation Therapy (SBRT) after First-line Systemic Therapy for Metastatic NSCLC  
Wake Forest Baptist Comprehensive Cancer Center  
WFBCCC # 62718

toxicities to be recorded along with the SAE. In addition, this nurse or coordinator is responsible for entering the adverse event information into the SAE console in WISER. Once the adverse event has been entered into the SAE console an email informing the entire DSMC will be generated.

**THESE REPORTING REQUIREMENTS APPLY TO any staff member on the study team for a WFBCCC Institutional Interventional trial. Ultimately, the protocol PI has the primary responsibility for AE identification, documentation, grading and assignment of attribution to the investigational agent/intervention. However, when an AE event as described above is observed, it is the responsibility of the person who observed the event to be sure that it is reported to the DSMC.**

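### After the 1-month visit, the only adverse-event question on the listed follow-up forms concerns radiotherapy complications, although the calendar requires immune toxicity to be graded in both arms

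*Combined protocol and SAP*

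**What the plan says.** The calendar in section 8.1 has one toxicity row, "RT-related Toxicities and Immunotherapy related toxicities", graded by CTCAE v5.0. It is marked at enrollment, at 1 month, "Every 3 mo For 3 years" and then every 6 months for 2 years, with no distinction by arm. For the 3- and 6-monthly visits the calendar lists Appendices G, J and L.

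- Appendix G records response and Appendix L records survival. Neither has an adverse-event item.
- Appendix J item 3 asks: "Were there any delayed patient complications related to the radiotherapy procedure since the last visit". The instruction beside it is "If yes, complete AE form". The remaining items cover chemotherapy, performance status, weight, height and new therapies.

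Adverse events are also collected by other routes:

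- Appendix F, at 1 month in both arms: "Did the subject have any adverse events in the last 30 days".
- Section 6.0: "CTC-AE measures will occur at each cycle of consolidation immunotherapy".
- Appendix R: "All Adverse Events (AEs) and Serious Adverse Events (SAEs) that occur on any patients enrolled on WFBCCC Investigator Initiated Interventional trials must be entered" in WISER.
- Appendix S is a log for any CTCAE term, with an attribution column.

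Adverse-event frequency is a secondary outcome (5.2.3) and is not limited to radiation effects. Section 14.2 commits to reporting acute and late toxicity descriptively.

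**The concern.** The calendar asks for two kinds of toxicity in two arms. The form used at most visits prompts for one kind, which in practice concerns one arm. Two consequences follow.

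First, once immunotherapy has stopped, a radiation patient is still asked about late toxicity, whereas a control patient with no radiotherapy has nothing to report under item 3.

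Second, item 3 requires a causal judgement before the event is recorded. The guidance in section 6.2 leans towards treating inflammatory events as immune-related unless another cause is clear. A physician following it could answer no for a late pneumonitis or colitis even in the radiation arm. Objective 2.2.3 names pneumonitis, gastrointestinal toxicity and hepatotoxicity, for which attribution to radiation or immunotherapy can be uncertain.

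At stake is whether late adverse-event frequencies in the two arms come from the same question. The protocol itself says of immunotherapy that "Autoimmune complications can potentially be life-threatening or permanent" (9.2), so late immune events are worth asking about.

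**Working it through.** The plan states no figure on this point, so there is none to reproduce. The check compares the adverse-event prompts and then counts the visits and patients exposed to the gap.

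**1. Prompts side by side**

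| Source | When it applies | Causes covered | Arms |
|---|---|---|---|
| Calendar row (8.1) | every follow-up visit | radiation and immunotherapy | both |
| Appendix F | 1 month only | any | both |
| Section 6.0 | each immunotherapy cycle | any CTCAE | both |
| Appendix J item 3 | follow-up visits | radiotherapy only | both on paper; generally radiation arm only in effect |
| Appendix R (WISER) | general duty to enter | any | both |
| Appendix S | log, laid out by cycle | any, with attribution | both |

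The calendar states the requirement. Appendix R and Appendix S say where events go once known. Only Appendix F, the per-cycle rule and Appendix J item 3 cause someone to ask, and of these only item 3 remains after the 1-month visit once infusions have ended.

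**2. Scheduled follow-up visits**

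- One at 1 month.
- Every 3 months for 3 years: 36/3 = 12.
- Every 6 months for 2 years: 24/6 = 4.
- Total: 1 + 12 + 4 = 17.

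Appendix F covers 1 of the 17. At the other 16, item 3 is the only adverse-event question on the listed forms.

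Maintenance immunotherapy is meant to total 2 years (8.5). Assume it ends 24 months into follow-up. The later visits are months 27, 30, 33 and 36, plus four 6-monthly visits: 4 + 4 = 8 of 17 with only the radiotherapy question. Doses before randomization count towards the total (Schema), which moves the end earlier. Dose delays (6.0) and the interval of up to 8 weeks after radiation (6.1) move it later. Each 3-month shift earlier adds one visit; each shift later removes one while visits remain 3-monthly. With early discontinuation the count can reach 16.

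**3. Patients in the gap**

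With 112 randomized 2:1 (13.1), the arms are 112 × 2/3 = 74.7 and 112/3 = 37.3. Patients who progress move to survival-only follow-up (8.4.2), so the gap concerns those who are progression-free and off immunotherapy.

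As an illustration, take the medians in 13.1 (8 and 15 months from first treatment) and assume exponential PFS, S(t) = 0.5^(t/median). Take about 27 months from first dose to the end of immunotherapy, roughly 3 months of initial therapy plus 24 of maintenance (also an assumption).

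- Control: 37.3 × 0.5^(27/8) = 37.3 × 0.096 = 3.6.
- Radiation: 74.7 × 0.5^(27/15) = 74.7 × 0.287 = 21.4.
- Total: about 25 of 112.

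Patients must be progression-free to be randomized. Conditioning on being progression-free at 6 months replaces 27 by 21:

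- Control: 37.3 × 0.5^(21/8) = 37.3 × 0.162 = 6.0.
- Radiation: 74.7 × 0.5^(21/15) = 74.7 × 0.379 = 28.3.
- Total: about 34 of 112.

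Patients who stop immunotherapy early, for toxicity or otherwise, stay in follow-up (8.5) and add to these counts. The documents give no rate for them.

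**The case against.** The strongest reply is that Appendix J is not the plan's safety system. The calendar tells sites to grade immune toxicity at each of these visits whatever Appendix J says, Appendix R obliges them to enter every adverse event, and Appendix S accepts any cause with attribution. A site that follows the calendar loses nothing. The safety analysis is descriptive with no between-arm test, and objective 2.2.3 is about the toxicity of adding radiation. The listed forms may also not be exhaustive: Appendices K, O, Q and S are in use without a calendar row, and the text of section 8.3 (Data Management Procedures) was not available.

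Much of this stands, and it rules out several stronger readings that a reader might infer:

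- *Immune toxicity is never prompted.* Appendix F and the per-cycle rule prompt for it in both arms.
- *Controls can only answer no.* CNS radiosurgery before randomization is possible in either arm (Schema), although item 3 seems aimed at protocol radiotherapy.
- *All 112 patients are affected, for at least 3 of 5 years.* Patients who progress leave this follow-up, and 3 years (5 − 2) is approximate, not a lower bound.
- *Late toxicity will look concentrated in the radiation arm.* That would require sites to record only what item 3 asks. It is a risk, not a certainty.
- *The rate above 10% for autoimmune complications in 9.2 measures the loss.* It is an overall risk with no timing.

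What the reply does not remove is the mismatch itself. A duty to record known events differs from a question asked at the visit, and the only such question on the listed late-visit forms differs in effect by arm and puts attribution first. No blinding is described that would offset this.

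**Conclusion.** The point holds as a form-to-calendar mismatch of limited reach. At the 3- and 6-monthly visits no listed form carries an all-cause adverse-event question. The gap matters chiefly for progression-free patients who have stopped immunotherapy: about 25 to 34 of 112 under exponential PFS, the protocol's medians and about 27 months to the end of therapy, plus early stoppers at an unstated rate. Only about 4 to 6 of those 25 to 34 would be controls. For such patients about 8 of 17 scheduled visits carry only the radiotherapy item, and up to 16 after early discontinuation.

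The result is a risk of unequal late-AE ascertainment between arms, and of missed immune events after treatment stops in both. The size of any bias cannot be computed from the documents. The primary outcome, power and alpha are unaffected. The change is worth making because it is almost free and because late events that nobody asked about may be hard to recover afterwards.

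**What to change.** Reword Appendix J item 3, for both arms, to: *Any new or worsened adverse event since the last visit, whatever the cause? If yes, complete AE form.* Record attribution only after the event is captured, in the existing attribution column of Appendix S, and identify there whether it refers to radiation, immunotherapy or another cause. Appendix F already asks an all-cause question, so this extends the plan's own practice to the later visits. The cost is one reworded item and slightly more adverse-event entry at visits that already take place.

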**Appendix K: Progression of Disease**

Has there been progression of disease _____ (Y/N)
Date of progression: _____/_____/_____(MM/DD/YYYY)
For patients randomized to the radiation arm: Is progression inside or outside prior RT field (defined by 50% Isodose line) _____ Organ site of progression? _____
For patients randomized to the immunotherapy alone arm: Is progression at a site of disease that was present prior to first line chemo-immunotherapy _____

A Randomized Trial of Consolidative Immunotherapy with vs without Thoracic Radiotherapy and / or Stereotactic Body Radiation Therapy (SBRT) after First-line Systemic Therapy for Metastatic NSCLC  
Wake Forest Baptist Comprehensive Cancer Center  
WFBCCC # 62718

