**2.2 Secondary Objective(s)**

- 2.2.1 We plan to estimate overall survival in all patients and will compare overall survival of those randomized to radiation and consolidative immunotherapy against those receiving consolidative immunotherapy alone.
- 2.2.2 In patients who experience subsequent failures after initiating protocol directed therapy, we will assess whether these failures occurred at known or new sites of disease.
- 2.2.3 We plan to evaluate toxicity associated with the addition of consolidative radiation therapy to upfront chemoimmunotherapy followed by additional consolidative immunotherapy. This will include calculating rates of adverse events depending on treatment site. Potential toxicities reported would include pneumonitis, esophagitis, chest wall pain, dermatologic toxicity, renal dysfunction, gastrointestinal toxicity including nausea, vomiting, and diarrhea, hepatotoxicity, and abdominal pain. These toxicities would be assessed according to site of irradiation by the treating physician and graded as per CTCAE 5.

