  - c. The schedule above is standard of care for imaging followup. Should a patient be enrolled after starting maintenance immunotherapy and after their first 3 month followup scan, then they may be allowed to switch to 6 months interval imaging at 3yrs from the end of chemo-immunotherapy, rather than a full 3 yrs from the date of randomization in accordance with standard of care. At discretion of treating oncologist.
7. Definition of 1 mo. or 30 day followup
  - a. For patients randomized to RT, this time point is considered 30 days +/- 14 days from end of all radiation therapy treatments
  - b. For patients randomized to immunotherapy alone, this time point is considered 30 days +/- 14 days from the end of the 2nd cycle of on protocol maintenance immunotherapy
8. Two tubes of whole blood may be collected at time of registration or any time prior to initiating any protocol directed therapy and at the 1 month follow up +/- 2 weeks.
9. If patients progress and are not eligible for randomization, or if they progress at any point on the study, they are only followed w appendix L for survival after the point of progression

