### For patients randomized to radiation:

Patients will undergo CT imaging of chest/abdomen/pelvis at 1 month after the last treatment of radiation is completed. Subsequently, they will undergo CT imaging of chest/abdomen/pelvis every 3 months for 3 years, then every 6 months for 2 years per standard of care.

**For patients randomized to continue maintenance immunotherapy:** alone, they will undergo CT imaging of chest/abdomen/pelvis at 1 month after the 2nd cycle of protocol directed maintenance immunotherapy has been delivered. Subsequently, they will undergo CT imaging of chest/abdomen/pelvis every 3 months for 3 years, then every 6 months for 2 years per standard of care.

Should a patient be enrolled after starting maintenance immunotherapy and after their first 3 month followup scan, then they may be allowed to

switch to 6 months interval imaging at 3yrs from the end of chemo-immunotherapy, rather than a full 3 yrs from the date of randomization in accordance with standard of care. At discretion of treating oncologist.

If a patient, has suspicion of progression but requires closer interval followup than 3 months or additional imaging, this is allowable at the discretion of the treating physician. If ultimately, they are deemed to not have progressive disease, they would then resume the schedule listed in the study calendar above.

**8.4.2** Patients who progress on or after protocol directed therapy will be followed for survival only as per Appendix L without further protocol follow up requirements. This includes progression of the protocol treated tumors, non-protocol treated tumors and the development of new metastatic disease. Tumor progression will be determined by RECIST criteria.

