**14.2 Analysis of Secondary Objective**

The proportions with local control (LC) of SBRT-treated lesions, and overall survival (OS) parameter estimates, both secondary outcomes, will be first examined in simple univariate and bivariate analyses (e.g., means, medians, 85% confidence intervals around key parameter estimates.). LC will be assessed only in patients with at least 4-months of radiographic follow -up. The reason for specifying a minimum of 4 months follow-up to score LC was to avoid uncertainty associated with early transient radiographic changes within the high dose region; patients who died without a minimum of 4 months post-SBRT imaging study follow-up are not considered evaluable for LC but are evaluable for PFS and OS.

Data will be collected for planned subset analysis of in-field local control of irradiated sites, progression-free and overall survival according to (1) tumor histology (adenocarcinoma vs other histology) and (2) response to initial chemotherapy (response vs stable disease).

In all randomized patients, time to progression at known sites of disease, as well as time to development of new disease sites, and number of new disease sites will be collected.

Overall survival comparison between the two randomized groups will be assessed with methods analogous to PFS described above in 13.1. Additionally, we will also examine OS in the group of patients who were enrolled but not randomized; however, we will not conduct statistical comparisons of this group with either randomized group.

All safety measures, including acute and late toxicity, will be reported using descriptive statistics (mean, median, SD, proportions, and 95% confidence intervals). This will include calculating frequency/risk of adverse events by treatment site. Potential toxicities reported would include pneumonitis, esophagitis, chest wall pain, dermatologic toxicity, renal dysfunction, gastrointestinal toxicity including nausea, vomiting, and diarrhea, hepatotoxicity, and abdominal pain. These toxicities would be assessed according to site of irradiation by the treating physician and graded as per CTCAE 5.

A Randomized Trial of Consolidative Immunotherapy with vs without Thoracic Radiotherapy and / or Stereotactic Body Radiation Therapy (SBRT) after First-line Systemic Therapy for Metastatic NSCLC  
Wake Forest Baptist Comprehensive Cancer Center  
WFBCCC # 62718

Reference List

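### Appendix K asks each arm a different question about where failure occurred, so known-versus-new-site failure cannot be put on one definition across arms from the visible forms

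*Combined protocol and SAP*

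**What the plan says.** Secondary objective 2.2.2 says that after a failure "we will assess whether these failures occurred at known or new sites of disease"; outcome 5.2.2 repeats this. Section 14.2 states that, in all randomized patients, data will be collected on "time to progression at known sites of disease, as well as time to development of new disease sites, and number of new disease sites". It separately mentions a "planned subset analysis of in-field local control of irradiated sites".

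Appendix K is the visible form for the location of failure. Radiation patients are asked "Is progression inside or outside prior RT field (defined by 50% Isodose line", and an organ field is printed on the same line. Patients on immunotherapy alone are asked "Is progression at a site of disease that was present prior to first line chemo-immunotherapy". The form has one progression date.

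Section 8.4.2 uses a finer split when it defines progression: "This includes progression of the protocol treated tumors, non-protocol treated tumors and the development of new metastatic disease". It also says that patients who progress "will be followed for survival only as per Appendix L without further protocol follow up requirements". Footnote 9 to the study calendar in section 8.1 agrees: "they are only followed w appendix L for survival after the point of progression".

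**The concern.** The two arms are classified against different reference points: the irradiated volume in one, disease before systemic therapy in the other. The objective asks about neither field nor isodose, and no visible rule converts in-field/out-of-field into known/new.

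This matters because the rationale in section 1.1 is that first failures tend to occur at original sites and that local therapy changes this pattern. The patterns-of-failure series cited there defines original sites as those present before systemic therapy, which matches the control question and not the radiation question. If an analyst equates 'outside' with 'new', a known but unirradiated site that fails counts as new in the radiation arm. The same failure in a control counts as known. Part of any apparent shift could then come from the form.

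**Working it through.** The plan gives no figure for failure pattern, so there is none to reproduce. The check compares the forms with the outcome and then bounds the artefact by assumption.

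**1. What each form supplies**

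| Needed for 2.2.2, 5.2.2 and 14.2 | Radiation arm | Immunotherapy-alone arm |
|---|---|---|
| Failing site present before first-line therapy? | Not asked | Appendix K |
| Failing site new? | Not asked; 'outside' mixes new and unirradiated known sites | Only as the negative of the item above |
| Number of new sites | Not asked | Not asked |
| Known and new together | No rule | No rule |
| Date | One progression date | One progression date |

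The other visible forms fill the gap only in part.
- Appendix D counts disease persisting after restaging, a later reference time than the control question, and locates only the extracranial sites to be treated.
- Appendix E describes irradiated extracranial tumours.
- Appendix G scores target and non-target lesions and has no new-lesion or location field.
- Organ is too coarse: a lung failure may be an old or a new lung lesion.

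**2. Size of the artefact (assumptions labelled)**

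Let k be the true share of failures at known sites, set equal in both arms so that any gap is artefact. Let u be the share of radiation-arm known-site failures lying outside the field. If inside is read as known and outside as new:

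apparent known share in the radiation arm = k × (1 − u); artefact = k × u.

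Two anchors for k come from section 1.1. Neither was measured in this population.
- Low: in the local-therapy arm of the cited randomised phase II trial, 1 locoregional plus 2 combined failures out of 13, so 3/13 = 23.1%. This is locoregional, not known-site, failure and serves only as a proxy.
- High: 64%, from the retrospective series after first-line systemic therapy.

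The range of u is assumed; the documents give none.

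| k | u = 10% | u = 25% | u = 50% |
|---|---|---|---|
| 23.1% | 20.8% (gap 2.3 points) | 17.3% (5.8) | 11.5% (11.5) |
| 64% | 57.6% (6.4) | 48.0% (16.0) | 32.0% (32.0) |

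**3. The opposite error**

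A new lesion can also arise inside the 50% isodose volume and be read as known. If a share v of new-site failures does so:

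apparent known share = k × (1 − u) + (1 − k) × v.

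With u = v = 10% and k = 64%: 0.576 + 0.036 = 61.2%, so the gap falls from 6.4 to 2.8 points. With k = 23.1%: 0.208 + 0.077 = 28.5%, which is 5.4 points in the other direction. The table above takes v = 0.

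**4. Which end is likelier**

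Criterion 3.1.6 requires persistent active disease to be amenable to radiation, and section 7.5 defines the gross tumour volume as all known disease. If both are followed, sites persisting at restaging are mostly in field, and out-of-field known failures are mainly sites that had resolved before randomization. That favours small u. It does not make u zero: section 8.4.2 expects some tumours not treated on protocol, and targets and dose are at the physician's discretion.

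**The case against.** The strongest reply is that little depends on this. Sections 2.2.2 and 5.2.2 promise to assess, 14.2 promises to collect, and no between-arm test of failure pattern is named. Section 14.2 already requires the site data in all randomized patients, so the form merely lags behind the plan. Appendix K's fields are blanks in which 'both' could be written. Source documents are sent centrally (9.6.1) and retained (9.6.5), and the overall principal investigator periodically reviews progression scoring at affiliate sites (9.6.4.2). Forms named in section 10.0, such as Patient Baseline Characteristics, are not reproduced, and section 8.3 was not available for this check. The in-field item is also right for its own purpose, local control of irradiated sites.

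Most of this stands, and it limits the point to a data-capture gap in a descriptive secondary outcome. It does not remove the gap: a form completed as printed still yields a measure whose meaning depends on the arm.

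A reader might go further and infer that the failure pattern is lost for good. The documents do not support that, because retained imaging and reports could be re-read. Nor do they support treating the mixed local-and-distant counts of the cited randomised trial as a measure of harm here: local/distant is not known/new, and nothing suggests that mixed failures would be coded in opposite directions by arm.

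**Conclusion.** The point holds as a mismatch between Appendix K and the outcome it serves. On the visible forms, known-versus-new-site failure cannot be put on one definition across arms without returning to source imaging, and the new-site count is missing in both arms.

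The size cannot be computed from the documents. Under the stated assumptions the artefact is about 2-12 points at a 23% known-site share and 6-32 points at 64%, probably toward the low end if persistent disease is irradiated as 3.1.6 and 7.5 suggest. The direction, toward the hypothesised shift, requires that 'outside' be read as 'new', which the documents never instruct, and that few new lesions arise inside irradiated volumes.

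A reader might infer that the primary comparison is compromised. It is not affected by this point: Appendix K takes the progression date in the same way in both arms. Whether event-free PFS should be censored at the last adequate tumour assessment rather than at last contact (section 8.10) is a separate, minor matter.

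**What to change.** 1. **Appendix K:** ask both arms the same items: organ; present before first-line therapy; present at randomization; new; number of new sites. Let known and new both be ticked. Keep the in-field question as an extra item for irradiated patients.
2. **Sections 2.2.2 and 5.2.2:** define 'known' once, with its reference time.
3. **Section 14.2:** state that known-site and new-site times refer to first progression, since follow-up is for survival only afterwards, and say how a mixed failure is counted. A formal competing-event analysis is optional for a descriptive outcome.

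The cost is one form revision and a few sentences, with no added scans or visits. For patients who have already progressed, the items must be abstracted from existing reports, including imaging from before first-line therapy. Only the pattern at first progression can be obtained.
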